				
addition of instructions on how to perform study evaluations and non-compulsory visits on site for the patient
 
addition of the Table (4.2.2) 3 about the conduct in case of definitive discontinuation of IMP during the double-blind period
 
 • Section 4.3: additional information about analysis to minimise bias • Section 4.4.1: clarification on the way of administration of the oral solution • Section 4.6: clarification on VABS II scale for source data • Section 5.2: Non-selection criteria 
modification of criterion 15
 
modification of the non-selection criterion 24 to further describe stabilised epilepsy
 
modification of non-selection criterion 25 with an information about alternative interventions
 
modification of the non-selection criterion 27 with a clarification for the use of laxatives
 
 • Section 5.4: Exclusion criteria 
modification of the exclusion criterion 34 (i.e. value of QT interval and value of hypercalciuria)

--	--	--	--	---

				
modification of exclusion criteria 35 (nephropathy)
 
 • Section 5.6.1: modification of withdrawal criteria for: Occurrence of seizures Proteinuria/creatininuria Value of hypercalciuria Value of QT prolongation Addition of absence of 2 consecutive planned urinary monitoring analysis • Section 5.6.2.Procedure Addition of information on withdrawal visit • Section 6.2: correction of two errors of IMPs dispensing (at W026) during the double blind period and the open label safety extension period • Section 6.3: addition of recommendations about the use of laxatives and use of light gas sedation • Section 7.2: information on who will be authorized to complete the VABS II • Section 8.2: Methods and measurement times information on training by the investigators on the C-SSRS-C and the PAERS, information on ECG reading process (centralised and locally), clarification on biological safety measurements clarification on the recommendation that investigators should encourage patients to eat foods containing potassium as soon as the patient is included in the study • Section 8.8: addition of
--	--	--	--	--

				
explanation about causal causal relationship
 
 • Section 8.9.2: addition of information about responsibility of the investigator • Section 8.9.3: addition of information about new safety information • Section 12.4: clarification of the section on Supervisory committee • Sections 13.2 and 13.3: clarification about assent/consent • Section 14.1: addition of information for the investigator after the final data base lock about participant data from his/her centre for archiving in the study file • Section 14.2: additional information about data collected on paper form (VABSII) on data entry and data validation • Section 14.3: Archiving: further clarification about archiving process • Section 18: REFERENCES: updating of references
	NA	12/12/2018	BRA	See appendix 22
	NA	13/03/2019	IRL	See appendix 23
	NA	26/03/2019	BRA	See appendix 24
	NA	27/03/2019	IRL	See appendix 25
	NA	26/04/2019	BRA	See updated appendix 24
	NA	30/07/2019	USA	See appendix 26
	3	12/08/2019	ALL	
 • Section 5.4. Exclusion criteria: updating of criterion 34 about abnormal urinary calcium/creatinine ratio (>0.85mmol/mmol of

				
creatinuria) and calciuria (≥ 3mmol/l)
 
 Section 5.6.1. Withdrawal criteria: updating of criterion about abnormal urinary calcium/creatinine ratio (>0.85mmol/mmol of creatinuria) and calciuria (≥ 3mmol/l)
	4	12/02/2020	FRA	See appendix 27
	5	14/02/2020	POL	See appendix 28
	6	03/08/2020	FRA	See updated appendix 27
	7	10/09/2020	POL	See updated appendix 28
	8	30/11/2020	ALL	
 Study summary sheet: update of Study completion date Addition of the signature of the Biostatistics Head Section 4.2.1. Study plan: update of the definition of the End of trial Section 4.2.2. Investigation schedule: update of the Table (4.2.2)1 and addition of the mention of CARS QPC questionnaire for the parents questionnaires (SRS2 and quality of life questionnaires) and update of table (4.2.2) 2 Update of the section 4.4.3. Management of the blinding systems Update of the section 5.6.1. for Special conduct in case of gastrointestinal

				
symptoms and weight loss
 
 • Section 8.2. Update of part about renal ultrasound • Section 9.1. Measurement of drug concentration: with cancellation of the sentence 'Thus, the exact PK sampling times cannot be specified' • Section 16. Ownership of the results – Data sharing policy and publication policy: update of the paragraph • Section 17.1.3. Final study report: addition of a primary clinical report after the 6-month double-blind period, a main clinical report after the 6-month open label period with the 6-week follow-up period and addition of an addendum to the report for the optional 6-month extension period • Addition of the appendix 29: Instruction to investigators for handling data rights requests
	9	25/03/2021	CZE	See appendix 30

STUDY SUMMARY SHEET

Name of the sponsor: I.R.I.S. [name]	Individual Study Table Referring to Part of the Dossier	(For National Authority Use only)
Name of Finished Product:	Volume:	
Name of Active Ingredient: Bumetanide (S95008)	Page:	
Title of study: Efficacy and safety of bumetanide oral liquid formulation in children aged from 2 to less than 7 years old with Autism Spectrum Disorder. A 6-month randomised, double-blind, placebo controlled multicentre parallel group study to evaluate efficacy and safety of bumetanide 0.5mg twice a day followed by an open label active 6-month treatment period with bumetanide (0.5mg twice a day) and a 6 weeks discontinuation period after treatment stop. Protocol No.: CL3-95008-002		
Coordinator(s) or Investigator: National coordinators and investigators: listed in a separate document		
Study centre(s): International multicentre study Total planned number of centres: Around 50 Total planned number of countries: 12		
Study period: 
 - Study duration for the participant: up to 66 weeks - Study initiation date (planned date of first visit first participant): Q3 2018 - Study completion date: (planned date of last visit last participant in the open label period or in the extension period, whichever occurs the latest) : Q4 2022 	Study development phase: III	
Objective(s): The primary objective is to demonstrate the superiority of bumetanide (0.5mg BID) oral liquid formulation compared to placebo in the improvement of ASD core symptoms using CARS-2 after 6 months of treatment in children aged from 2 to less than 7 years old presenting with a confirmed ASD diagnosis. The secondary objectives are: 
 - To assess the effect of bumetanide on the secondary efficacy endpoints - To assess the safety of bumetanide - To confirm the acceptability and palatability of the oral liquid formulation - To describe the bumetanide effects on patients quality of life - To improve existing pharmacokinetic model of bumetanide in this population The exploratory objective is to describe the Bumetanide effect on utility index scores		
Methodology: Study design: 6-month, randomized, double-blind, placebo-controlled, parallel groups followed by an open label active 6-month treatment period with bumetanide.		
Number of participants: Planned: 200 patients included Total for each treatment (approximately): 100 in bumetanide group, 100 in the placebo group		
Diagnosis and main criteria for inclusion: 
 - Male and female patients from 2 to less than 7 - Primary diagnosis of ASD as per DSM-5 criteria - Criteria met for ASD on Autism Diagnostic Observation Schedule-Generic (ADOS-2) and Autism Diagnosis Interview Revised (ADI-R) - CGI (Clinical Global Impression) – Severity rating Score ≥ 4 - Childhood Autism Rating Scale second edition (CARS2-ST or HF) total raw score ≥ 34 - Social responsiveness Scale second edition (SRS-2) total score ≥ 66 T-Score - Absence of diagnosis of Fragile X or Rett Syndrome - Absence of any clinically significant abnormality likely to interfere with the conduct of the study according to the judgment of the investigator. 		

Name of the sponsor: I.R.I.S. [name]	Individual Study Table Referring to Part of the Dossier	(For National Authority Use only)
Name of Finished Product:	Volume:	
Name of Active Ingredient: Bumetanide (S95008)	Page:	
Test drug: BUMETANIDE oral solution dosed at 0.5 mg/mL - For patients with a weight < 25 kg: bumetanide 0.02mg/kg corresponding to 0.04ml/kg oral liquid formulation taken twice daily (in the morning at wake up and in the afternoon 3 hours before going to bed at the latest) - For patients with a weight ≥ 25kg: bumetanide 0.5mg corresponding to 1mL oral liquid formulation taken twice daily (in the morning at wake up and in the afternoon 3 hours before going to bed at the latest)		
Comparator: PLACEBO - For patients with a weight < 25 kg: 0.04ml/kg oral liquid formulation taken twice daily (in the morning at wake up and in the afternoon 3 hours before going to bed at the latest) - For patients with a weight ≥ 25kg: 1mL oral liquid formulation taken twice daily (in the morning at wake up and in the afternoon 3 hours before going to bed at the latest)		
Duration of treatment: Run-in period: up to 4 weeks (without IMP) Study treatment period (with IMP administration): 52 weeks (+/- 28 days) Follow up period: 6 weeks after discontinuation of IMP		
Criteria for evaluation: Efficacy measurements: Primary efficacy endpoint: CARS2 total Raw score, expressed mainly in terms of change from baseline to 6 month Secondary efficacy endpoints: 
 - The change in each individual CARS2 domain from baseline to 6 month - The change in SRS-2 total raw score from baseline to 6 month - CGI-I score at 6 month - The change in Vineland Adaptive Behaviour Scale II (VABS II) from baseline to 6 month Safety measurements: 
 - Adverse events, Pediatric Adverse Event Rating Scale (PAERS) - Clinical laboratory evaluation: biochemistry including electrolytes monitoring, haematology, , calciuria, creatininuria, proteinuria, - Vital signs and clinical examination: weight, height, Body Mass Index, heart rate, blood pressure - Electrocardiogram - Renal ultrasound - Suicidality: Columbia-Suicide severity scale Children's version (C-SSRS-C) Other measurements: 
 - Acceptability and palatability assessments - Paediatric Quality of Life Inventory (PedsQL) - WHOQOL-Bref questionnaire - Utility index score on the EQ-5D-3L Pharmacokinetic measurements: 
 - Concentrations of bumetanide will be determined in plasma by Cephac, using a validated bioanalytical method based on a protein precipitation followed by reverse phase liquid chromatography with tandem mass spectrometric detection. Procedures will be described in a separate bioanalytical protocol established by the assay centre. 		
Statistical methods: Efficacy analysis:		

Name of the sponsor: I.R.I.S. [name]	Individual Study Table Referring to Part of the Dossier	(For National Authority Use only)
Name of Finished Product:	Volume:	
Name of Active Ingredient: Bumetanide (S95008)	Page:	

All efficacy analyses will be performed in all randomized patients. The primary endpoint is defined as the change from baseline to 6 month in CARS2 total score. Primary analysis: bumetanide will be compared to placebo using a general linear model with baseline CARS2 and stratification factors as covariates. Missing data handling: CARS values post treatment discontinuation due to adverse event or lack of efficacy will be imputed using a reference based multiple imputation with a jump-to-reference approach. This approach assumes treatment benefit in patients who discontinue the Bumetanide arm disappears immediately upon discontinuation. Treatment effect estimation will take into account the situations when a patient can no longer tolerate or benefit from the treatment (occurrence of AE, lack of efficacy). CARS values post treatment discontinuation due to others reasons will be imputed using a classic multiple imputation approach assuming these patients could have theoretically continued to be treated without being put at undue risk. Sensitivity analysis: to assess the robustness of the results of the primary analysis, sensitivity analyses to the method of handling missing data will be performed including a mixed model for repeated measurement (MMRM).
 
Study participants (disposition, baseline characteristics and follow-up) and Safety analysis: Safety analysis: Safety analyses will be performed in the Safety Set defined as all included patients having taken at least one dose of study treatment. For every safety measurements, descriptive statistics will be provided by treatment groups.
 
Pharmacokinetic analysis: A population pharmacokinetic analysis will be performed to assess PK profiles of bumetanide in children. The population PK analysis will provide population PK parameters and their associated variability. In this analysis, the potential influence of covariates will be also investigated. Individual secondary PK parameters (such as AUC_{12,ss}, C_{min}) will be derived from the model for each patient. The population PK analysis will be detailed in a separate Data Analysis Plan. Exploratory assessment of the relationship between exposure and pharmacodynamics (efficacy and potentially safety) will be performed and if applicable, population PK/PD models will be developed and a Data Analysis Plan will be set up.
		
Contractual signatories		

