- All those measures contribute to the installation of a ritual much appreciated by patients with ASD.
- Sponsor highly recommends that the same person in charge of study evaluations follows a given child during the study in order to minimize any potential bias in study assessments and to reduce the burden linked to the potential stress suffered by the child.
- Paediatric liquid formulation has been specially developed for this paediatric clinical program. This formulation showed a good acceptability and palatability profile in the phase II.

For the benefit of the study, bumetanide could be the first pharmacological candidate allowing the treatment of ASD core symptoms in paediatric population, acting on a key component of the disease pathophysiology (alteration of GABAergic neurons and circuits, the conversion of GABA-mediated neuronal excitation into inhibition during maturation of specific neuronal populations being reported to be altered in neurodevelopmental diseases such as autism).

Acting centrally as a NKCC1 inhibitor, bumetanide provokes reduction of intracellular chloride, switching the aberrant excitatory action of GABA into an inhibitory action, and therefore may restore important developmental capacities.

Consequently, as there is no drug treatment for core symptoms of ASD, we set up a study with bumetanide in young developing patients with ASD in order to reduce the ASD core symptoms and functional impairment and to improve quality of life. Studies are needed in paediatric population, childhood being a time when brain plasticity is at the greatest and where behavioural and educative interventions could have the most benefit.

For the risk for the patient, the safety profile of bumetanide is similar to that reported for other loop diuretics. The target organ is the kidney and the safety profile is related to the potent diuretic activity of the compound. Based on the safety experience gained at this stage of drug development in ASD (5 clinical studies described above), the safety profile of bumetanide in ASD children and adolescents seems comparable to the one observed in adult patients treated for oedema. Despite the penetration of bumetanide into brain, no toxic effects on the Central Nervous System have been observed.

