4. STUDY DESIGN

4.1. Endpoint(s)

Table (4.1) 1 - Endpoints

	Objectives	Endpoints
Primary	To demonstrate the superiority of bumetanide (0.5mg BID) oral liquid formulation as compared to placebo in the improvement of ASD core symptoms after 6 months of treatment in children aged from 2 to less than 7 years old with ASD	Childhood Autism Rating Scale, Second Edition (CARS2) total raw score. Main expression will be change from baseline to 6 month.

	Objectives	Endpoints
Secondary	To assess the effect of bumetanide on the other efficacy endpoints	
 - The change in SRS-2 total raw score from baseline to 6 month - CGI-I score at 6 month - The change in VABS II subscores from baseline to 6 month - The change in each individual CARS2 domain from baseline to 6 month
	To assess the safety of bumetanide	
 - Adverse events (AE), Paediatric Adverse Event Rating Scale (PAERS) - Clinical laboratory evaluation - Vital signs and clinical examination: weight (kg), height (m), Body Mass Index (BMI) (kg/m²), systolic blood pressure (mmHg), standing, sitting; Diastolic blood pressure (mmHg), standing, sitting, heart rate (bpm) - Electrocardiogram - Renal ultrasound - Assessment of suicidal ideation and suicidal behaviour using the Columbia Suicide Severity Rating Scale Children's version (C-SSRS-C)
	To confirm the acceptability and palatability of the oral liquid formulation	Acceptability and palatability questionnaire
	To describe the bumetanide effects on patients' quality of life	
 - Paediatric Quality of Life Inventory (PedsQL) expressed in term of change from baseline to month 6 - WHOQOL-Bref questionnaire summarized at each planned visit for each period using descriptive statistics
	To improve existing pharmacokinetic model of bumetanide in this population	PK points at W012 and W026
Exploratory	To describe the Bumetanide effect on utility index scores	Utility index score on the EQ-5D-3L

Refer to sections 6.1 and/or 7.1 for further details.

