5.6. Participant withdrawal

5.6.1. Withdrawal criteria

Premature discontinuation of IMP during the double blind treatment period (W000-W026) does not mean that the participant prematurely stops the participation in the study.

In the case of premature discontinuation of IMP during the double blind period and, if the patient does not require an important modification on his/her current background medical care, he/she will be invited to complete CARS2, SRS-2, CGI evaluations and AE assessment for W012 (if discontinuation occurs prior to W012) and W026 visit as planned in the investigation schedule (Section 4.2.2).

Important modification of current medical care is defined as follows:

- *Newly initiated formal behavioural, cognitive or cognitive-behavioural therapy*
- *Increase/decrease weekly prescribed hours >25% of behavioural, cognitive or cognitive-behavioural therapy*
- *Newly initiated or recently changed pharmacotherapy:*
 - o *Introduction of a psychotropic medication (considered as forbidden in the study, section 6.3)*
 - o *Introduction or dose increase of an antipsychotic*
 - o *Introduction or dose increase of ADHD treatment*

The following criteria will lead to a premature discontinuation of IMP:

- Serum potassium levels < 3mEq/L
- Any suicide attempt, whatever its severity
- High suicidal risk, according to investigator's judgment or with a suicidal ideation of 4 or 5 on C-SSRS-C
- Nephrocalcinosis observed at the renal ultrasound
- Occurrence of seizure(s)
 - o in a patient without any medical history of seizure.
 - o or in a patient with a medical history of seizure if this require any modification of the on-going anti-epileptic treatment.
- Any symptoms or signs of potential renal function failure.
- eGFR $\leq 80\text{mL}/\text{min}/1.73\text{m}^2$ (estimated glomerular filtration rate, Schwartz formula 2009).
- Clinically relevant nephropathy according to investigator's clinical judgment (based on broader sources including risk factors, medical history, clinical examination and biological parameters).
- Clinically relevant hypercalciuria.

In case of abnormal urinary calcium/creatinine ratio that may be the expression of a clinically relevant hypercalciuria, a retest should be performed as soon as possible. Based on these results, the investigator should have a discussion with the local paediatric nephrologist in order to assess whether it corresponds to the presence of a clinically

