8.2. Methods and measurement times

The **Columbia Suicide Severity rating Scale Children's version (C-SSRS-C)** ([Posner, 2007](#)) ([Posner, 2011](#)) assesses suicidal ideation and suicidal behaviour. Investigator will complete an e-training on this tool prior to the study start.

The C-SSRS-C includes two forms:

- Baseline/Screening version: completed at W000

- Since Last Visit version: to be completed at W012, W026, W038, W052 or at the withdrawal visit in case of premature withdrawal

The **Paediatric Adverse Event Rating Scale (PAERS)** (Shapiro, 2009) is an inventory report designed to identify signs/symptoms experienced by the patient since the study treatment initiation. Investigator will complete an e-training on this tool prior to the study start.

The PAERS will be completed:

- o During the Double Blind period at: W000, W000+Day 17, W004, W008, W012, W016, W020, W026 visits
- o During the Open Label period at: W026+Day17, W030, W034, W038, W042, W046, W052 visits
- o At the withdrawal visit in case of premature withdrawal

PAERS includes three forms:

- Youth form, to be completed when possible by the patient,
- Parent form, to be completed by a parent/legal representative or caregiver (when applicable).
 - o As far as possible same person should complete the form during the study
- Clinician form filled after assessment of youth form and parent forms

Physical examinations

- DBP, SBP and heart rate must be always assessed. Appropriate conditions are assessment in a sitting or lying position after 5-minute rest and at 1mn after standing position (orthostatic hypotension: known effect of bumetanide):
 - o At Selection
 - o During the Double Blind period at: W000, W002, W012, W026 visits
 - o During the Open Label period at: W028, W038, W052 visits
 - o At the withdrawal visit in case of premature discontinuation.DBP and SBP will be measured with the specific device provided by the Sponsor for the study.
- Body weight must be assessed:
 - o At Selection
 - o During the Double Blind period at: W000, W000+Day17, W004, W008, W012, W016, W020, W026 visits
 - o During the Open Label period at: W026+Day17, W030, W034, W038, W042, W046, W052 visits
 - o At the withdrawal visit in case of premature withdrawal.
- Height must be assessed:
 - o At Selection
 - o During the Double Blind period at: W012, W026 visits
 - o During the Open Label period at: W038, W052 visits
 - o At the withdrawal visit in case of premature withdrawal

12-lead ECG

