- During the Double blind treatment period it will be prescribed at W020 and the assessment of the recording must be available for/during at W026 visit
- During the Open label treatment period it will be prescribed at W046 and the assessment of the recording must be available for/during at W052 visit
- At the withdrawal visit in case of premature withdrawal.

This exam could be done within 7 days prior to the day of the visit.

This exam should be assessed by a nephrologist or by a qualified specialist who will transmit the renal assessment to the investigator. As far as possible the same nephrologist/qualified specialist will assess renal ultrasound exams for a given patient all along the study.

Biological Safety measurements

To ensure homogeneity of the results, all biological assessments (except Na⁺/K⁺ parameters under treatment) will be carried out by the central laboratory chosen by I.R.I.S. The reference values of measured parameters will be mentioned in each laboratory report.

Biological results will be sent to site from central laboratory via a laboratory report, with the exception for Na⁺/K⁺ parameters which will be assessed locally (except at the selection visit before the first IMP intake and at the withdrawal visit (WD) after the last IMP intake. All laboratory reports (central and local) should be assessed by investigator and kept in the patient's medical file.

The sampling process and storage conditions on site will be described in the laboratory manual provided by the central laboratory.

The laboratory tests will be performed:

- Selection visit (laboratory tests will be prescribed at), so that the results are available for the inclusion visit
- During the double blind treatment period at W000+48/72h (only Na⁺/K⁺), W000+Day10 (only Na⁺/K⁺), W000+Day17 (only Na⁺/K⁺), W004 (only Na⁺/K⁺), W012 and W026 visits
- During the open-label extension period, at W026+48/72h (only Na⁺/K⁺), W026+Day10 (only Na⁺/K⁺), W026+Day17 (only Na⁺/K⁺), W030 (only Na⁺/K⁺), W038 and W052 visits
- At the withdrawal visit in case of premature withdrawal

The results should be checked carefully by investigator once received, and the patient/parent/legal representative(s) or caregiver (when applicable) should be contacted again to inform them about results and any abnormality that necessitates a specific follow-up.

Laboratory tests at Selection visit

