1.2.1. Study plan

The study is divided into the following periods:

- A run-in period without treatment up to 4 weeks (from ASSE to W0) to allow investigators to perform ECG, renal ultrasound, laboratory examinations and to respect the wash-out period of any unauthorised treatment before inclusion.
- A double-blind period of 6 months (from W000 to W026): at W000, patients are randomised (1:1) in double-blind conditions to one of the two treatment groups: bumetanide or placebo.
- An open-label period of 6 months (from W026 to W052):
 - Patients randomised in the S95008 arm during the double-blind period will continue to be treated by S95008 during the whole open-label period.
 - Patients randomised in the placebo arm during the double-blind period will receive bumetanide during the whole open-label period.
- A follow-up period of 6 weeks after treatment discontinuation (from W052 to WEND). A WEND visit should be planned 6 weeks after Investigational Medicinal Product (IMP) stop (W052 or premature withdrawal).
- A 6-month optional extension period with Bumetanide is proposed in some countries where it is not possible to supply Bumetanide (study formulation) at the end of the follow up period via a Named Patient Basis (NPB) access or a Post-Access Study Program. This extension is optional and proposed to the patients based on the investigator's clinical judgement (clinical benefit observed during the main study without no major safety concern).

IMPs are supplied as two oral administrations per day with 1 mL graduated pipette upon waking in the morning and in the afternoon, 3 hours before going to bed at the latest.

[figure not shown]
The volume of the oral solution will be adapted according to a body-weight basis for patients with a weight lower than 25 kg.

The appearance and taste of the solution are the same for all IMPs throughout the study. The first IMP intake takes place on the day of the inclusion visit in the afternoon.

An adaptation of the oral solution volume according to the weight of the patients will be performed during the study at visits W012, W026 and W038.

The study plan is shown in [Figure \(1.2.1\) 1](#).

Figure (1.2.1) 1 - Study plan

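### Renal ultrasound and PAERS are declared safety endpoints, but neither Protocol 10.2.2.6 nor SAP 3.6 plans a stand-alone summary of them, and the adverse event tables only partly fill the gap

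*Protocol*

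**What the plan says.** **What is declared.** The synopsis lists the safety measurements, including "Electrocardiogram - Renal ultrasound - Suicidality: Columbia-Suicide severity scale", and names the PAERS beside adverse events. Protocol Table (4.1) 1 repeats this under the secondary safety objective. One bullet there opens "Adverse events (AE), Paediatric Adverse Event Rating Scale (PAERS", and renal ultrasound has a bullet of its own. For all of these the synopsis undertakes: "For every safety measurements, descriptive statistics will be provided by treatment groups".

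**What is collected.** Under Protocol 8.2, renal ultrasound is done at selection, W026, W052 and the withdrawal visit. For the double-blind scan, "it will be prescribed at W020 and the assessment of the recording must be available for/during at W026 visit". The PAERS is completed "During the Double Blind period at: W000, W000+Day 17, W004, W008, W012, W016, W020, W026 visits", then at seven open-label visits and at withdrawal.

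**Why the kidney is singled out.** The background section says of the drug's safety: "The target organ is the kidney". Section 5.6.1 includes among the reasons to stop study drug: "Nephrocalcinosis observed at the renal ultrasound".

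**What is analysed.** SAP 3.6 covers adverse events, C-SSRS-C, laboratory values, vital signs and ECG. Renal ultrasound appears in the SAP only in section 1.2.1, where the run-in is there "to allow investigators to perform ECG, renal ultrasound, laboratory examinations and to respect the wash-out period". The PAERS does not appear in the SAP text available for review.

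**The concern.** The double-blind period is the only randomised period. Placebo children move to bumetanide at W026, so the by-arm comparison of W026 scans cannot be rebuilt from later data. If the SAP is followed as written, the report can show by-arm adverse events and laboratory shifts. It has no planned table of how many children were scanned in each arm, how many scans were abnormal, or how many changed from baseline. The repeated symptom inventory likewise has no planned table. A reader of the report would get less kidney-safety information than the synopsis promises, although an ultrasound finding is itself a reason to stop study drug.

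**Working it through.** No figure in the plan needs reproducing. The check sets each declared safety endpoint beside the section that should analyse it.

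**Step 1: coverage of Table (4.1) 1.**

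| Declared safety endpoint | Protocol 10.2.2.6 | SAP 3.6 |
|---|---|---|
| Adverse events | 10.2.2.6.1 | 3.6.1 |
| PAERS (same bullet) | none | none |
| Laboratory | 10.2.2.6.2 | 3.6.3 |
| Vital signs, clinical examination | 10.2.2.6.3.1 | 3.6.4.1 |
| ECG | 10.2.2.6.3.2 (listing) | 3.6.4.2 (descriptive summaries) |
| Renal ultrasound | none | none |
| C-SSRS-C | none | 3.6.2 |

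Of six bullets, ultrasound is missing entirely and the adverse event bullet is half covered. The gap starts in the protocol's own statistics section. The SAP did add to that section elsewhere, with a C-SSRS-C analysis and fuller ECG summaries, so following the protocol's structure does not explain the omission. No passage available for review records a decision to drop either endpoint.

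**Step 2: can the adverse event tables stand in?** Protocol 8.3 makes an abnormal examination finding an adverse event if the investigator considers it clinically relevant. It also includes worsening of an existing condition and relevant events from a safety scale. SAP 3.6.1 tabulates TEAEs, and TEAEs leading to withdrawal of study drug, by arm in the Safety Set. So part of the information does arrive. Three things do not:

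- findings that the investigator does not judge relevant;
- a denominator of children actually scanned, because the adverse event tables use all treated children;
- a baseline-to-W026 shift of the scan result.

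**Step 3: timing.**

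- The withdrawal visit may take place up to 7 days after the last dose (Protocol 5.6.2).
- The double-blind TEAE window closes at last intake + 2 days at the latest (SAP Table (3.6) 1, period #2).
- Days 3 to 7 after the last dose therefore lie outside the window: 7 − 2 = 5 of the 7 days allowed.
- Over the longer period #1, SAP 3.6.1 tabulates only serious events and deaths.

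A non-serious finding first seen at a withdrawal scan on days 3 to 7 is therefore in no by-arm adverse event table and is at most listed. For a child who stops early, Protocol 4.2.2 asks at the later W012 or W026 visit only for CARS2, SRS-2, CGI and adverse events. The withdrawal scan is thus that child's last planned double-blind scan.

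A W026 scan in a child still on drug does not have this problem. It is done before or at the visit and falls inside the window.

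**The case against.** The strongest reply is that little of importance would be lost.

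- Nephrocalcinosis on ultrasound stops study drug, and a finding with that consequence is hard to call clinically irrelevant. It should appear by arm among TEAEs, including those leading to withdrawal. *This stands.* A reader might infer that the trial would give no between-arm information on nephrocalcinosis. The documents do not support that.
- A reader might also infer that new or worsened findings are not counted. Both the adverse event definition and the SAP's emergence rules include worsening, so the defect is only that scan results are not counted systematically.
- The PAERS works as a structured prompt, and relevant events from it can be adverse events. It would be wrong to describe adverse event capture here as merely spontaneous. *This stands*, but the synopsis still promises a summary of the scale itself.
- Exclusion criterion 34 names nephrocalcinosis and other ultrasound abnormalities, so baseline scans should be largely clean. A shift table would then show mainly incident findings. *This stands in part*: incident findings per child scanned are exactly what is missing.
- Kidney function is covered by by-arm laboratory tables, including creatinine, calciuria and proteinuria. *This is true*, but those tables do not summarise imaging.
- The table templates are a separate document and may contain these outputs. *This cannot be checked.* The SAP describes itself as the place where the planned analyses are set out, so the specification belongs there in any case.

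**Conclusion.** The inconsistency is real and of moderate weight. Two declared safety measurements have no stand-alone summary in Protocol 10.2.2.6 or SAP 3.6, contrary to the synopsis. The adverse event route recovers part of the content, but it depends on investigator judgement, lacks a scan denominator and a baseline shift, and has a gap after the 2-day window that falls on children who stop early.

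The timing point rests on two readings. One is that the one-week limit in Protocol 5.6.2 also governs the withdrawal visit of a child who stops drug but stays in the study. The other is that the scan is done at that visit. Section 8.2 allows it up to 7 days earlier, so some withdrawal scans will fall inside the window.

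The documents give no rate of ultrasound abnormality, so no statement about how many cases would be missed is supported. The randomisation, sample size and primary analysis are not affected.

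**What to change.** Add to SAP 3.6, for the double-blind period, by arm in the Safety Set:

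1. **Renal ultrasound.** Number of children scanned, and number and percentage with normal, abnormal and nephrocalcinosis results, at baseline and at W026 or, failing that, the withdrawal scan. Count the withdrawal scan whether or not it falls within last intake + 2 days. Add the number and percentage with new or worsened findings, a shift table and a listing.
2. **PAERS.** One compact table with the number and percentage of children for whom each item is new or worsened from W000 at any double-blind visit. An item-by-visit display is not needed.

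Under SAP 3.6 the open-label and combined safety analyses are each single-arm, so any versions for those periods are description only. Bring Protocol 10.2.2.6 into line. If the sponsor prefers not to add these tables, the SAP should state and justify the omission, and the synopsis should be corrected.

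The cost is a few extra descriptive tables from assessments the protocol already requires. No test, visit or clinical rule changes.
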